### **3.5. Method of Assigning Subjects to Treatment Groups**

On Day 1, subjects will be randomized to receive placebo, NYX-783 50 mg QD, or NYX-783 10 mg QD in a 4:1:1 ratio, respectively. Placebo responders and placebo non-responders (CAPS-5 total score reduction from baseline  $\leq 35\%$  and total CAPS-5 total score  $\geq 26$  at Week 4) will be identified at the completion of Stage 1 (Weeks 1-4) in a blinded fashion; then, each group (i.e., placebo responders and placebo non-responders) will be re-randomized in a blinded fashion to placebo, NYX-783 50 mg QD, NYX-783 10 mg QD in a 3:2:2 ratio, respectively, for Stage 2 (Weeks 4-8).

treatment. Subjects who received active treatment during Stage 1 will receive placebo in Stage 2.

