## 4. Statistical Analysis and Reporting

### 4.1. Introduction

Data processing, tabulation of descriptive statistics, calculation of inferential statistics, and graphical representations will be performed primarily using SAS (release 9.4 or higher).

Continuous (quantitative) variable summaries will include the number of subjects (n) with non-missing values, mean, standard deviation (SD) (or standard error (SE) if appropriate), median, minimum, and maximum. Confidence intervals (CIs) will be added if appropriate.

Categorical (qualitative) variable summaries will be based on frequencies and percentages.

Unless stated otherwise, efficacy data for endpoints included in mixed effects repeated measures model (MMRM) analyses (groups [1], [2], [3], [7], [8], and [9]) will be summarized by visit and treatment group (Placebo, NYX-783 10 mg QD, NYX-783 50 mg QD) to allow for summary data treatment comparisons as per model inference.

Efficacy data for Stage 2 groups [4], [5], [6], [10], and [11] will be presented separately.

Unless stated otherwise, safety data will be summarized by Stage and treatment group (Placebo [as Placebo Only and Placebo Stage 2, separately], NYX-783 10 mg QD, NYX-783 50 mg QD); data presented by visit will be displayed based on the treatment group which applies at onset for AEs/collection date.

The minimum and maximum will be reported with the same degree of precision (i.e., the same number of decimal places) as the observed data. Measures of location (mean and median) will be reported to 1 degree of precision more than the observed data and measures of spread (SD, SE) will be reported to 2 degrees of precision more than the observed data.

Percentages will be presented to 1 decimal place, unless otherwise specified.

Unless otherwise indicated, all statistical tests will be conducted at a 0.10 significance level using one-sided tests and p-values will be reported. Corresponding 80% CIs (the interpretation of which is equivalent to a one-sided 90% CI when restricted to a single bound) will be presented.

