##### 6.1.3.1. Handling of Missing Date Values

###### Partial or Missing Dates

The following conventions will be used to impute missing portions of dates for AEs. An AE with missing or incomplete start dates will be reported as treatment emergent for both Stages unless data provided clearly indicates an onset as occurring within a particular Stage (e.g. a month specific to Stage 1) or outside of the treatment-emergent period (e.g. year provided is prior to first dose of study drug) as defined in Section [6.1.4](#).

Partially available concomitant medication dates will be handled similarly with respect to identifying use as concomitant as defined in Section [9.7](#).

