- Sheehan Suicidality Tracking Scale (S-STS) = The standard version of the S-STS is a 16-item scale that assesses the seriousness of suicidality phenomena on a Likert-type scale (0 to 4) ranging from 0 = “not at all” to 4 = “extremely.” The S-STS score will be derived by data-management. The S-STS accommodates a wide range of timeframes. In clinical trials, the frequently used variants are “in the past week”, “in the past month”, “since the last visit”, “lifetime look back”, and “in the past day.” In this study, during screening, "in the past month" version is used. For all the other visits "since the last visit" version of the S-STS is used.
- Subjects with high S-STS scores- Subjects with a score of 3 or 4 on any questions 2, 3, 4, 5, 6, 7, 8 or 13 in the S-STS questionnaire will be flagged.

- Placebo Non-responder = A Placebo Non-responder must satisfy the following criteria.
  - Randomized to placebo in Stage 1 of the study
  - Week 4 whose CAPS-5 total score reduction from baseline [Day 1]  $\leq 35\%$  and Week 4 CAPS-5 total score is  $\geq 26$
- Change from baseline = value at current visit – value at baseline (as defined in Section 6.1.1).
- TEAE = this is any adverse event with an onset date on or after first dose of study drug through 7 days after last dose of study drug. The Stage in which an event is considered treatment emergent will also be determined based on the relative onset timing against the first dose of Stage-specific study drug. Adverse Events with an onset during the 7 days after end of Stage 2 will be part of Stage 2.
- Duration of reported treatment period (years): For displays of TEAEs, it may be necessary to standardize rates of events due to variable treatment reporting periods. For Stage-specific reporting, durations are computed based on (the date of the last dose of study drug - the date of the first dose of Stage-specific study drug + 1).
- Treatment Related AEs= For each reported AE/SAE, the investigator assesses the relationship to study drug and categorize them into the following categories: Not Related = Unrelated and Unlikely Related, Related = Possibly Related and Probably Related). If an assessment is missing, then it will be treated as Related.
- Sexual Abuse= this is used to flag subjects who were victims of sexual abuse. If the medical history term preferred term is ‘Sexual Abuse’ or ‘Victim of Sexual Abuse’ then those subjects will be flagged as victim of sexual abuse.

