### 9.1. Adverse Events

The number, percentage and incidence rate of subjects reporting treatment emergent AEs (TEAEs), grouped by MedDRA system organ class (SOC) and preferred term (PT) (coded using MedDRA v21.1), will be tabulated by Stage, and treatment group. In the case of multiple occurrences of the same TEAE within the same subject and Stage, a subject will only be counted once for each PT or SOC. Similar methods will be used to provide summaries further reported by severity and relationship. In the summaries reporting severity and relationship to study medication the event with the maximum severity and strongest relationship will be reported, respectively. For these analyses, missing severity and relationship will be imputed as described in Section 6.1.3.2.

The frequency, percentage, and incidence rate of subjects reporting TEAEs, will be reported as described for the following summaries:

- TEAEs by SOC and PT
- TEAEs by SOC, PT, and maximum severity
- Treatment-related TEAEs by SOC and PT
- Treatment-related TEAEs by SOC, PT, and maximum severity

An overall summary of TEAEs, TEAEs leading to discontinuation of study, serious TEAEs, Severe or life-threatening TEAEs, and fatal AEs will be reported. This summary will also be reported for treatment-related TEAEs. Overall summaries for TEAEs and

treatment-related TEAEs by maximum severity will also be provided. The number of total events at each level of TEAE reporting will also be used in the calculation of incidence rate per subject-years of study participation given the specified Stage and reporting treatment period (total events/total patient-years included in the reported treatment period). In general, the duration of the reported treatment period is based on the amount of time a subject has taken the assigned drug within each Stage of reporting for a specified treatment; this is described in more detail in Section 6.1.4.

Missing and partially missing AE start and/or stop dates will be used to determine TEAE status for reporting, according to the specifications described in Section 6.1.5.

In the AE data listings, all AEs will be displayed. AEs that are not treatment-emergent will be flagged.

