## 9.2. Adverse Events of Interest

The following are AEs of interest.

- Suicidality (ideation or attempt)
- Abuse and/or dependency events (drug & alcohol)
- Dissociative experience events
- Depression (or worsening depression)

The following AEs are also of potential clinical interest

- Eating disorder
- Nightmares (or worsening nightmares)
- Anxiety (or worsening anxiety)
- Panic attack
- Self-injurious behavior
- Aggressive behavior toward others
- Negative social events (e.g. loss of job, separation from significant other)

A summary of incidence rates (frequencies and percentages) by SOC, and preferred term will be prepared for all adverse event of interest listed above. The summary will be presented for each Stage as described in Section 9.1.

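### The SAP's stage-specific duration ties only the first dose to the stage, so Stage 1 person-time would be nearly doubled and Stage 1 adverse event rates nearly halved if it is programmed as written

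*SAP*

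**What the plan says.** SAP 6.1.4 (Derived Variables) defines the duration of the reported treatment period, for stage-specific reporting, as "the date of the last dose of study drug - the date of the first dose of Stage-specific study drug + 1". The stage qualifier is attached to the first dose and not to the last.

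The entry just above it, for treatment-emergent events, uses the same unqualified last dose to close the whole treatment period. It places an event in a stage by its onset relative to the first stage-specific dose.

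SAP 9.1 says that "the duration of the reported treatment period is based on the amount of time a subject has taken the assigned drug within each Stage" and refers to 6.1.4 for more detail. The event rate it plans to tabulate by stage and treatment group is "total events/total patient-years included in the reported treatment period".

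On what happens between the stages, SAP 3.5 says: "Subjects who received active treatment during Stage 1 will receive placebo in Stage 2". Stage 1 placebo subjects are re-randomised 3:2:2 to placebo, 50 mg and 10 mg.

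**The concern.** Section 9.1 states the intent and 6.1.4 gives the rule to be coded. Followed literally, that rule adds all Stage 2 dosing time to the Stage 1 denominator, while the Stage 1 numerator is limited by onset date. Numerator and denominator then cover different periods and different treatments:

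- In the Stage 1 active arms, all of the added time is on placebo.
- In the Stage 1 placebo arm, about 4/7 of the added time is on NYX-783.

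Stage 2 durations come out correctly, because for those subjects the last dose overall is the last Stage 2 dose. The error therefore falls on Stage 1 alone. At stake are the absolute Stage 1 rates per patient-year and any reading of Stage 1 rates beside Stage 2 rates, in a study whose overarching goal begins with safety and tolerability.

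**Working it through.** The documents state no person-time or event rate, so there is no planned figure to reproduce.

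**Inputs**
- Stage 1 dosing Days 1 to 28 and Stage 2 dosing Days 29 to 56, so 28 days each (Protocol 9.5 and 9.7; SAP 7.4).
- N = 156, randomised 4:1:1, giving 104 placebo and 26 per active arm (SAP 3.2 and 3.5).
- Dropout 15% in Stage 1 and 11% in Stage 2 (SAP 3.2). I take the 11% as a share of those entering Stage 2.
- Assumption, not in the documents: dropouts leave mid-stage, after 14 days of that stage.

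**A completer.** Within the stage: 28 − 1 + 1 = 28 days. As written: 56 − 1 + 1 = 56 days. The ratio is 2.00, with no dropout assumption needed.

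**One active arm, n = 26**
- Finish Stage 1: 26 × 0.85 = 22.1. Leave in Stage 1: 3.9.
- Leave in Stage 2: 22.1 × 0.11 = 2.431. Complete both stages: 19.669.
- Within stage: 22.1 × 28 + 3.9 × 14 = 673.4 days = 1.84 years.
- As written: 19.669 × 56 + 2.431 × 42 + 3.9 × 14 = 1258.2 days = 3.44 years.
- Inflation: 1258.2 / 673.4 = 1.868. Rate error: 1 − 1/1.868 = 46.5% too low.

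**Placebo arm, n = 104** (four times the above)
- 2693.6 days = 7.37 years within stage; 5032.7 days = 13.78 years as written.
- Extra time 6.40 years, of which 6.40 × 4/7 = 3.66 years on NYX-783.

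**Sensitivity**

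| Setting | Inflation | Stage 1 rates too low by |
|---|---|---|
| Stage 1 dropouts leave on day 28, Stage 2 dropouts on day 1 of the stage | 1.76 | 43% |
| Base case, mid-stage | 1.87 | 46% |
| Stage 1 dropouts leave on day 1, Stage 2 dropouts on day 28 of the stage | 1.99 | 50% |
| 11% taken as a share of all randomised, mid-stage | 1.86 | 46% |
| Stage lengths varied from 25 to 31 days, mid-stage | 1.70 to 2.08 | 41% to 52% |

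**Between arms within Stage 1.** The factor on the rate is within-stage time over as-written time. With Stage 2 dropout held at 11%, it is 0.5206 for 5% Stage 1 dropout and 0.5624 for 30%. Even that contrast moves a rate ratio by only 0.5624 / 0.5206 = 1.080, about 8%.

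**Between stages.** Suppose the true risk is equal and constant, and events are captured for 7 days after the last dose (for dropouts in Stage 1, for everyone in Stage 2).
- Stage 2 rate factor: (26.46 + 7) / 26.46 = 1.265, where 26.46 = 28 × (0.89 + 0.11 × 0.5).
- Stage 1 rate factor as written: (673.4 + 3.9 × 7) / 1258.2 = 700.7 / 1258.2 = 0.557. With the last dose tied to the stage: 700.7 / 673.4 = 1.041.
- Apparent Stage 2 to Stage 1 ratio: 1.265 / 0.557 = 2.27 as written, and 1.265 / 1.041 = 1.22 once corrected.

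**The case against.** The best reply is that this is a dropped modifier. The sentence opens by restricting itself to stage-specific reporting, which could be read to govern both dates, and 9.1 states the meaning outright. A programmer who reads the two together would probably not put Stage 2 placebo days into an active-arm denominator. The table shells, which are not part of these documents, may settle it. All of that is possible. But 9.1 sends the reader to 6.1.4 for the detail, and the neighbouring entry uses the unqualified last dose for the end of all treatment. The literal reading is therefore the one the SAP's own usage supports, and two readings that differ nearly two-fold should not be left to the programmer.

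Three further points stand in part:

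- The 1.87 and 46% depend on an assumed dropout timing. The completer figure does not.
- No Stage 1 versus Stage 2 rate comparison or test of event rates is specified. But the rates will be tabulated by stage, and readers will compare them.
- SAP 4.1 speaks of the "treatment group which applies at onset for AEs/collection date", but that clause concerns data presented by visit. The mismatch rests instead on the 6.1.4 rule that places events in a stage by onset.

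**Conclusion.** The definition in 6.1.4 is wrong as written and conflicts with 9.1. If coded literally, it makes Stage 1 event rates per patient-year about 46% too low under planned dropout with mid-stage timing, and 43% to 50% too low over all dropout timings with 28-day stages. The error is about the same in every Stage 1 arm if dropout is similar.

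The harm is limited. Counts and percentages of subjects with events are not affected. Nor are the summaries in SAP 9.2 and 9.2.1, where the term incidence rate means something else: "A summary of incidence rates (frequencies and percentages) by SOC, and preferred term will be prepared". This should be corrected before programming, but it does not threaten the trial's main conclusions.

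**What to change.** In SAP 6.1.4, add the qualifier Stage-specific to the last-dose term, so that duration is the date of the last Stage-specific dose minus the date of the first Stage-specific dose plus 1. Because the variable is labelled in years, also state the conversion from days (365.25 was used here). This brings 6.1.4 into line with 9.1. It costs a few words and changes no data collection.

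Two smaller mismatches are separate from the formula and merit a clarifying sentence each:

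- The SAP states that "Adverse Events with an onset during the 7 days after end of Stage 2 will be part of Stage 2", while person-time stops at the last dose. A Stage 2 completer thus has about 35 days of event capture over 28 days of person-time.
- Under Partial or Missing Dates, "An AE with missing or incomplete start dates will be reported as treatment emergent for both Stages unless" the available data settle the onset. Such an event can therefore enter both numerators.

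Both are deliberate conventions. The SAP need only say how they bear on the rates.

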## **7. Study Patients/Subjects and Demographics**

Unless specified otherwise, summaries defined in this section will be presented by Stage based on treatment groups defined in Section 4.1 and in total within each reporting period.

### **7.1. Disposition of Patients/Subjects and Withdrawals**

The summary of subject enrollment and disposition will display the number of subjects who are screen failures (Stage 1), the number and percentage of subjects randomized, treated, completed and discontinued in each Stage. Specific reasons for discontinuation will be summarized according to the reasons listed on the eCRF. Percentages will be calculated based on randomized subjects in each Stage and overall.

The number of subjects enrolled, screen failures, randomized, treated and entering Stage 2 will be also tabulated by site. This summary will be reproduced Over All Stages.

For each stage and overall, each analysis population will be described.

All subject disposition data and analysis population details will be presented in data listings. Screen failure data will also be listed.

### **7.2. Protocol Violations and Deviations**

Prior to database lock, the protocol deviations will be reviewed for the following reasons:

- Standard study terminology deviation categories assigned
- Severity (major versus minor) assigned
- If a subject should be excluded from the PP population

Documentation will be put into place around the determination of patient population prior to lock and unblinding.

After database lock it may be determined that additional protocol deviations occurred, but could not be known prior to database lock. For example, a subject receiving study drug for the wrong treatment arm (i.e., a treatment arm other than the one they were randomized to). As a result, any additional protocol deviations found after database lock will be included with previous protocol deviations and documented separately to ensure timing of deviation is identified.

A subject listing will include the planned treatment arm, deviation category, protocol deviation, occurrence date with the corresponding study day, severity (major versus minor), and if the protocol deviation resulted in excluding a subject from the PP population. A frequency distribution table will be created to summarize only major protocol deviations by the assigned deviation categories.

### **7.3. Demographics and Other Baseline Characteristics**

Demographic and other baseline characteristic data including gender, age, height, weight and BMI will be summarized using descriptive statistics. For the continuous variables, the number of non-missing values and the mean, standard deviation, minimum, median and maximum will be tabulated.

Categorical data for age group, race, sex, ethnicity, family status, education and employment will be summarized by counts and percentages.

Time since start of PTSD (months) will be summarized. Similar descriptive statistics will be used to summarize the baseline clinical measures such as CAPS-5, PCL-5, HADS, CGI-S, PSQI and PSQI-A.

Treatment differences in subject characteristics at baseline (based on Stage 1 treatment groups), will be assessed using Chi-square test (or Fisher's exact test in case Chi-square does not fit the data) for categorical variables and Type III sums of squares analysis of variance (ANOVA) for continuous variables. For continuous variables, in case normality is not assessed a Kruskall-Wallis test will be performed.

These analyses will be performed on both the ITT Population using assigned treatment and SAF Population using actual treatment received for Stage 1 and Stage 2. For SAF Stage 1 analysis, actual treatment received during Stage 1 will be used for treatment group. For SAF Stage 2 analysis, actual treatment received during Stage 2 will be used for treatment group and placebo will be splitted in Placebo Only and Placebo Stage 2.

The number and percentage of subjects reporting types of medical histories will be tabulated by MedDRA system organ class and preferred term (coded using MedDRA v.21.1). This analysis will be conducted by Stage 1 treatment groups for the SAF.

All baseline characteristics data, including medical and disease history, as well as diagnosis information, will be reported in data listings.

### **7.4. Exposure and Compliance**

The first dose of study drug in Stage 1 will be administered orally at the investigative site. Subsequent study drug administration will be conducted on an outpatient basis. Stage 2 dosing begins the day after the Week 4 visit. Subjects will be instructed to take 1 capsule per day with water. A digital video dosing verification system for self-administration of investigational product (AiCure) was used to track capsule ingestion, and day and time of self-administration. This system is independent from EDC so a spreadsheet containing its information will be included in the statistical analysis of compliance. Cumulative counts for the total number of capsules dispensed; taken; returned and lost; subject compliance; as well as the duration of treatment will be summarized by actual treatment received (placebo [regardless of Stage 1 assignment], NYX-783 10 QD, and NYX-783 50 QD). The percentage of subjects who were compliant in each Stage will also be presented based on the SAF population. A subject will be considered compliant if between 80% and 120% of their expected dose had been taken.

Exposure and compliance data will be listed.

## 8. Efficacy Analysis

Unless specified otherwise, all efficacy analyses will be based on the ITT Population by treatment group (Placebo, NYX-783 50 mg and NYX-783 10 mg).

### 8.1. Primary Efficacy Analysis

The sequential parallel comparison design (SPCD) is an adaptive design that allows for re-randomization of placebo subjects (both "non-responders" and "responders") from an initial stage of the study to placebo or active treatment in a subsequent stage of the trial. In this study, data from the "all-comers" population of Stage 1 arms [1 = placebo], [2 = NYX-783 50 mg QD], [3 = NYX 783 10 mg QD] and the subpopulations of "placebo non-responders" in Stage 2 arms [7 = placebo], [8 = NYX-783 50 mg QD], [9 = NYX 783 10 mg QD] are pooled to yield a single p-value for treatment comparison.

#### 8.1.1. CAPS-5

The primary efficacy endpoint is change in CAPS-5 total score and subscores following 4 weeks of treatment in each respective Stage (Stage 1 [baseline to Week 4] and Stage 2 [Week 4 to Week 8]). Changes from baseline for specific visits and treatment groups will be used for the comparison of NYX-783 to placebo as described in Section 6 (for specification of visit alignment) and Section 6.1.1 (for information on baseline derivations). Modeled data will consist of change from baseline data through Week 4 for all of those randomized to treatment arms 1, 2 or 3 for Stage 1; and change from Week 4 assessment data for subjects randomized to arms 7, 8, or 9 for Stage 2.

The primary efficacy endpoint will be evaluated using the weighted combination of the estimated treatment effects from the Stage-specific mixed models for repeated measures (MMRM). The MMRM models will include variables for treatment group, visit, treatment-by-visit interaction term, baseline CAPS-5 score as covariate, and baseline-by-visit interaction. An unstructured covariance matrix will be used. If the model fails to converge with an unstructured covariance matrix other structures will be tried and the structure with the lowest corrected Akaike information criterion (AICC) will be used for the analysis. Full details will be included in the CSR. The Kenward-Roger approximation will be used to adjust the denominator degrees of freedom.

The treatment effect will be assessed as the differences in least-squares mean (LS mean) changes from baseline to Week 4 (Stage 1) and from Week 4 to Week 8 (Stage 2) for the NYX-783 50 mg QD, NYX-783 10 mg QD, and placebo groups defined in Section 8.1. A pairwise comparison will be made between each of the NYX-783 arms and placebo. The treatment effect will be pooled across Stages 1 and 2 using pre-specified 0.6/0.4 weighting for Stage 1/Stage 2.

Combined inference is computed using the weighted linear combination of stage-wise test statistics:

$$Z_{Combined} = \frac{0.6\widehat{\delta}_1 + 0.4\widehat{\delta}_2}{\sqrt{0.6^2Var(\widehat{\delta}_1) + 0.4^2Var(\widehat{\delta}_2)}}$$

Where,  $\widehat{\delta}_1$  is the estimated Stage 1 treatment effect and  $\widehat{\delta}_2$  is the estimated Stage 2 treatment effect. The combined test statistic  $Z_{combined}$  is used to compute the overall one sided treatment effect p-value.

LS means, 80% CIs (the interpretation of which is equivalent to a one-sided 90% CI when restricted to a single bound), and SEs for the mean CAPS-5 scores by visit and treatment group within each Stage will be estimated based on the separate MMRM models. This inferential analysis will also be performed for estimation of the following mean CAPS-5 treatment differences within each Stage:

- placebo vs NYX-783 10mg QD
- placebo vs NYX-783 50mg QD
- placebo vs NYX-783 10mg QD + NYX-783 50mg QD

One-sided P-values for these Stage-specific differences will be reported based on individual t-tests but no formal statistical inferences are planned for these results.

These analyses will be repeated for each subscore.

Descriptive statistics for observed CAPS-5 total score, subscores and their relative changes from baseline will also be tabulated by study visit and treatment group as described in Section 4.1 for the groups specified in Section 8.1.

CAPS-5 scores will also be presented graphically by treatment at each visit based on mean plots.

The following pseudo SAS code will be used to implement the MMRM analyses

```
proc mixed data=xxx ;
  class trt avisit subjid;
  model change = trt avisit trt*avisit caps5b caps5b*avisit
  / s ddfm=kenwardroger
  repeated avisit /subject = subjid type=un;
  lsmeans avisit * trt / diff=all cl alpha=0.2
run;
```

